14.4.6 Statistical analysis plan (SAP)

Before the final analysis, a SAP will be prepared by the trial statistician and approved by the principal investigator. It will describe in detail the analyses to be performed. Deviations from the analyses as specified above will be discussed with the study coordinators and can only affect the exploratory analyses, but not the primary (confirmatory) analysis on which the sample size is based. All analyses except the primary analysis should be considered as hypothesis-generating only.

14.4.7 Data and Safety monitoring board

A data and safety monitoring board will be installed before start of the study.

15 Registration and Randomization

15.1 Regulatory Documentation

Required regulatory and administrative documents must be provided to the HOVON Data Center before shipment of study drug and before enrolment of the first patient. This will always include an Ethics Committee approval for the investigational site. The HOVON Data Center will provide each investigator with an overview of the required documents. Each investigational site will be notified when all requirements are met and enrolment can start

15.2 Registration

Eligible patients should be registered before start of treatment. Patients need to be registered at the HOVON Data Center by one of the following options:

- ◆ Trial Online Process (TOP, <https://www.hdc.hovon.nl/top>). A logon to TOP can be requested at the HOVON Data Center for participants.
- ◆ By faxing the completed registration/randomization CRF [name] Monday through Friday, from 09:00 to 17:00 CET
- ◆ By [contact] Monday through Friday, from 09:00 to 17:00 CET

The following information will be requested at registration:

- ◆ Protocol number
- ◆ Institution name
- ◆ Name of caller/responsible investigator
- ◆ Local patient code (optional)
- ◆ Sex
- ◆ Year of birth
- ◆ Date written informed consent
- ◆ Specific items patient gives consent for (see ICF)
- ◆ Eligibility criteria

All eligibility criteria will be checked with a checklist.

Each patient will be given a unique patient study number (a sequence number by order of enrolment in the trial). Patient study number and result of randomization will be given immediately by TOP or phone and confirmed by fax or email.

Local Patient Code is a code that may be assigned to the patient by the investigational site for local administrative purposes. The code may be up to 8 characters long (letters and numbers allowed). The code should be in compliance with privacy regulations. It should not contain identifying data, such as patient initials or the complete hospital record number. The local code will be visible in the confirmation messages sent by TOP to local participants after registration of the patient. The key to this local patient code should only be accessible by the local investigator and the local hospital staff. Using or entering a local patient code is not obligatory.

15.3 Randomization

Patients achieving MRD negativity after cycle 12 (peripheral blood) and at day 15 of cycle 15 (peripheral blood and bone marrow), are randomized between continuous ibrutinib treatment until toxicity or progression and treatment free observation. Patients not reaching MRD negativity are not randomized and continue ibrutinib treatment until toxicity or progression.

Randomization has to occur within 14 days after MRD testing after day 15 of cycle 15.
Patients need to be randomized at the HOVON Data Center as described above for registration.

The following information will be requested at randomization:

- ◆ Protocol number
- ◆ Institution name
- ◆ Name of caller/responsible investigator
- ◆ Patient study number
- ◆ Response after cycle 12 and cycle 15

Patients will be randomly assigned to maintenance ibrutinib or observation arms through 1:2 randomization process with stratification at randomization by center, comorbidity (CIRS ≤ 6 vs >6), and TP53 aberration (TP53 mutation and or del(17p), no vs yes) with a minimization procedure, ensuring balance within each stratum and overall balance.

Result of randomization will be given immediately by TOP or phone and confirmed by fax or email.

15.4 Late registration of MRD positive patients who will continue with ibrutinib

Eligibility to continue ibrutinib for patients who are MRD positive at cycle 12 and/or 15 should also be registered at the HOVON Data Center. If the patient appears to be MRD positive, please fill in the randomization form and e-mail it to [contact]. It is not possible to register these patients in TOP.

16 Data collection and quality assurance

16.1 Case Report Forms

Data will be collected on *electronic* Case Report Forms (CRF) to document eligibility, safety and efficacy parameters, compliance to treatment schedules and parameters necessary to evaluate the study endpoints. Data collected on the CRF are derived from the protocol and will include at least:

- ◆ Inclusion and exclusion criteria;
- ◆ Baseline status of patient including medical history and stage of disease;
- ◆ Timing and dosage of protocol treatment;
- ◆ Baseline concomitant diseases and adverse events;
- ◆ Parameters for response evaluation;
- ◆ Any other parameters necessary to evaluate the study endpoints;
- ◆ Survival status of patient;

- ◆ Reason for end of protocol treatment.

Each CRF page will be identified by a trial number, and a combination of patient study number (assigned at registration) and hospital name.

The e-CRF will be completed on site by the local investigator or sub-investigator or an authorized staff member. The CRF must be signed by the local investigator or sub-investigator upon completion by means of an electronic signature. All CRF entries must be based on source documents.

Written instructions for completing the CRF will be provided by the HOVON Data Center. Access to the e-CRF will be provided by the HOVON Data Center only to authorized site staff members who have completed a training course on the use of the e-CRF. Training materials will be provided by the HOVON Data Center.

16.1.1 Rapid reporting of events

In this trial two types of rapid request forms will be used:

- ◆ Bleeding and atrial fibrillation are events of special interest which will be actively requested for in patients treated with ibrutinib. For this purpose a short questionnaire will be generated – a Rapid Request Form -, which will be sent by email to the local investigators. The form needs to be filled out every 3 months for as long as the patient is on ibrutinib treatment (i.e. 15 months for patients randomized to stop treatment, until end of protocol treatment for patients who continue ibrutinib treatment).

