Patients randomized to arm B who become MRD positive or have symptomatic CLL according to IWCLL criteria during the observation period reinitiate treatment with both ibrutinib and venetoclax for 12 cycles and continue ibrutinib treatment until toxicity or progression.

Only patients randomized for observation (arm B) are considered for the primary endpoint without formal comparison between arms.

Duration of treatment

All patients receive ibrutinib + venetoclax (with delayed start

and ramp up of venetoclax from cycle 3) for the first 15 cycles.

Thereafter Ibrutinib maintenance until progression/toxicity or observation without treatment.

Patients randomized to arm B who become MRD positive or have symptomatic CLL according to IWCLL criteria during the observation period reinitiate treatment ibrutinib + venetoclax for 12 months and continue ibrutinib treatment until toxicity or progression.

Subsequently all patients will be followed until 7 years after registration

Target number of patients	207 eligible patients. In order to take into account possible dropout due to ineligibility, 230 patients will be registered
Expected duration of accrual	Expected start of recruitment Q2/2017 Expected end of recruitment Q2/2020
Main study endpoints	
Primary endpoints: (Only considered for arm B of the study)
 
 - Proportion of patients fulfilling the criteria for progression free survival (PFS) at 12 months after stopping therapy (27 months after starting treatment) for patients randomized to stop treatment , reinitiated treatment due to MRD positivity not considered progression (see section 13.1 for details). 
Secondary endpoints (for all treatment groups):
 
 - Minimal residual disease (MRD) at 12 months after stopping treatment (month 27) for patients randomized to stop treatment, - PFS (IWCLL criteria), - Time to and number of patients reinitiating treatment, - Time to treatment failure after reinitiated treatment, - Time to next CLL treatment, - MRD after cycle 12 (PB), day 15 cycle 15 (PB and

- BM) and at later time points in PB,
- Overall survival (OS),
- Complete response (CR)/ Partial Response (PR)/ Stable disease (SD) after cycle 3, 9, 12, 15 and month 27 and 51 (3 years after stopping treatment),
- Duration of response,
- Safety parameters: Type, frequency, and severity of
 - o adverse events (AEs) and

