Secondary objectives (Arm B group)

- Time to and number of patients reinitiating treatment,
- Time to treatment failure after reinitiated treatment.

7 Study design

This study is designed as a phase 2 study with a late randomization in patients MRD negative after cycle 12 and 15, no formal comparisons between the two randomized treatment arms will be made.

During the treatment period all patients receive 15 cycles (28 days each) of oral ibrutinib + venetoclax treatment. During the first 2 cycles, only ibrutinib 420 mg a day is administered. From day 1 in cycle 3, ramp up over five weeks of venetoclax from 20 mg per day to the target of 400 mg per day is administered.

Patients achieving MRD negativity after cycle 12 in peripheral blood (PB) and at day 15 of cycle 15 in PB and bone marrow (BM) are randomized 1:2 between continuous ibrutinib treatment until toxicity or progression (arm A) and treatment free observation (arm B). Patients not reaching MRD negativity after cycle 12 and/or at day 15 of cycle 15 continue ibrutinib treatment until toxicity or progression (non-randomized patients).

MRD negative patients will be closely monitored for relapse/progression during the first 3 years after randomization by means of rapid reporting as described in section 16.1.1.

Patients becoming MRD positive (defined as $MRD \geq 10^{-3}$ and at least one month later $MRD \geq 10^{-2}$), or have symptomatic CLL according to IWCLL criteria (appendix A) during the observation period reinitiate treatment with both ibrutinib and venetoclax for 12 cycles and continue ibrutinib treatment until toxicity or progression.

Patients failing on reinitiating therapy (not reaching any response (CR/PR/SD) according to IWCLL criteria as assessed by the local investigator after 3 cycles of reinitiated therapy (or after reinitiation therapy until 12 months after randomization if progression occurred within 9 months from randomization) are considered as having progressive disease and will go off protocol treatment.

Details of all treatments (dose and schedule) are given in section 9.

8 Study population

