BM aspirate								X		X		X
Lymph node biopsy												X ³

1 If not performed earlier

2 Patients becoming MRD pos. retest 1 month later (only during observation)

3 If accessible lymph node is present

4. MRD and CT should be done at day 15 cycle 15 to have results available to assess SD, PR, CR, MRD neg at end of cycle 15.

Table 10.2.3 Required investigations during/after reinitiation treatment¹

	Before start of reinduction treatment	Extra at end of cycle 3	Extra at end of cycle 12	After cycle 12: Every 3 months for 2 years, every 4 months for 3 rd year	Extra at 1 year after cycle 12	After month 51 ²	Progressive disease
Medical history	X			X		X	
Adverse events	X			X		X	
Physical examination	X			X		X	X
TLS risk category (appendix G)	X						
Lab tests							
Hematology	X			X		X	X
Blood chemistry	X			X		X	
Additional chemistry	X						
Bone marrow							
Bone marrow biopsy			X		X		
(PET)-CT scan	X		X		X		X
(Clinical) response evaluation		X	X		X	X	X
Quality of Life²	X						
CENTRAL LAB							
Flowcytometry PB (or BM if PB not done)							X
FISH/CGH and NGS PB							X
MRD (flowcytometry)							
PB			X	X	X		X
BM aspirate			X		X		X
Side studies							
PB			X		X		X
BM aspirate			X		X		X
Lymph node biopsy							X ³

1 Note that the required investigations from month 27 as mentioned in table 10.2.1 are required for all patients

2. Follow the original schedule: quality of life at 1, 2 and 3 years after start maintenance/observation

3. If accessible lymph node is present

Medical history

Standard medical history, including:

- B symptoms
- Concomitant diseases
- Concomitant medications
- Adverse events

At entry

- Proven CLL or SLL by minimal required markers (CD19/CD20/CD5/CD23/Kappa/Lambda)
- Cumulative Illness Rating Score (see appendix F)
- Binet classification (see appendix A)
- Charlson comorbidity index (CCI)

Physical examination

Standard physical examination including body weight and height, with special attention for:

- Vital signs (Blood pressure, body temperature, pulse)
- WHO performance status (see appendix C)
- Palpable lymph nodes, spleen and liver sizes

Hematology

- Hemoglobin
- Leukocyte count
- Differential count
- Platelets count

At entry and on indication:

- DAT (direct antiglobulin test/Coombs test)
- PT
- PTT

Blood chemistry

- Creatinine clearance (calculated see appendix E)
- Bicarbonate
- Haptoglobin
- AST or ALT
- Bilirubine
- LDH

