12.1 Definitions

Adverse event (AE)

An adverse event (AE) is any untoward medical occurrence in a patient or clinical study subject administered a medicinal product and which does not necessarily have a causal relationship with the treatment.

An AE can therefore be any unfavorable and unintended sign (including an abnormal laboratory finding), symptom, or disease temporally associated with the use of a medicinal (investigational) product, whether or not related to the medicinal (investigational) product.

Adverse event of special interest (AESI)

Atrial fibrillation and bleeding events are adverse events of special interest in this trial, and will be actively requested for.

Serious adverse event (SAE)

A serious adverse event is defined as any untoward medical occurrence or effect that at any dose:

- ◆ Results in death
- ◆ Is a life-threatening event (i.e. the patient was at immediate risk of death at the time the reaction was observed)
- ◆ Requires hospitalization or prolongation of an existing hospitalization
- ◆ Results in significant or persistent disability or incapacity
- ◆ Is a congenital anomaly or birth defect
- ◆ Is an *important medical event* (i.e. important adverse events that are not immediately life threatening or do not result in death or hospitalization but may jeopardize the patient or may require intervention to prevent one of the above characteristics/consequences, including suspected transmission of infectious agents by a medicinal product).

Note: TLS is *an important medical event* in this trial which must be reported as SAE.

Suspected unexpected serious adverse reaction (SUSAR)

All **suspected** Adverse Reactions which occur in the trial and that are both **unexpected** and **serious**.

Suspected adverse reactions (AR) are those AEs of which a reasonable causal relationship to any dose administered of the investigational medicinal product and the event is suspected. Unexpected adverse reactions are adverse reactions, of which the nature, or severity, is not consistent with the applicable product information (e.g. Investigator's Brochure for an unapproved IMP or Summary of Product Characteristics (SPC) for an authorized medicinal product).

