13.2 Secondary endpoints

Secondary endpoints (for all treatment groups: MRD positive non-randomized patients, patients MRD negative after cycle 12 and at day 15 of cycle 15 randomized for ibrutinib maintenance (arm A) or observation (arm B)):

- ◆ Minimal residual disease (MRD) at 12 months after stopping treatment (month 27) for patients randomized to stop of treatment.
- ◆ PFS of all study groups.
- ◆ Time to and number of patients reinitiating treatment
- ◆ Time to treatment failure after reinitiated treatment
- ◆ Time to next CLL treatment
- ◆ MRD after cycle 12 (PB), at day 15 of cycle 15 (PB and BM) and at later time points in PB
- ◆ Overall survival (OS)
- ◆ Complete response (CR)/ Partial Response (PR)/ Stable disease (SD) after cycle 3, 9, 12, 15 and month 27 and month 51 (3 years after stopping treatment)
- ◆ Duration of response
- ◆ Safety parameters: Type, frequency, and severity of
 - adverse events (AEs) and
 - adverse events of special interest (AESI) and their relationship to study treatment
- ◆ Health-related quality of life (QoL) by EORTC QLQ-C30 and QLQ-CLL16 questionnaires
- ◆ Exploratory endpoints:
 - ◆ Evaluation of relationship between various baseline markers and clinical outcome parameters
 - ◆ Various markers at time of progression
 - ◆ Correlation between MRD in BM and PB
 - ◆ Correlation between MRD in BM and PFS/OS
 - ◆ Correlation between MRD in PB and PFS/OS

14 Statistical considerations

This study is designed as a phase II study with upfront registration and a late randomization for patients who are MRD-negative at 12 and 15 cycles. The primary objective of the study is to evaluate in arm B the efficacy of ibrutinib + venetoclax (VI) in terms of PFS 12 months after stopping treatment for patients achieving MRD negativity after cycle 12 and at day 15 of cycle 15 in previously treated patients with CLL (arm B). The patients in arm A and the non-randomized patients are only considered for secondary and exploratory endpoints, and no formal comparison between randomized patients are made.

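### Section 16.1.1 contradicts itself on the quarterly bleeding and atrial fibrillation form for arm B patients who restart ibrutinib

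*Protocol*

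**What the plan says.** Section 16.1.1 states the general rule: "The form needs to be filled out every 3 months for as long as the patient is on ibrutinib treatment". A footnote to Table 10.2.1 repeats it without a time limit. In 16.1.1 a bracket follows that explains what the rule means: "15 months for patients randomized to stop treatment, until end of protocol treatment for patients who continue ibrutinib treatment".

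Section 7 provides that arm B patients who become MRD positive or have symptomatic CLL "reinitiate treatment with both ibrutinib and venetoclax for 12 cycles and continue ibrutinib treatment until toxicity or progression". Section 9.4 and the synopsis also return these patients to ibrutinib. Their visits are set out in Table 10.2.3, "Required investigations during/after reinitiation treatment", which has an adverse events row but no Rapid Report Form row.

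On the purpose of the form, section 12.1 says: "Atrial fibrillation and bleeding events are adverse events of special interest in this trial, and will be actively requested for". Section 13.2 makes "adverse events of special interest (AESI) and their relationship to study treatment" part of the secondary safety endpoint for all groups. Section 14.4.2 tabulates toxicity after cycle 15 separately for MRD-positive patients, arm A and arm B.

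Section 7 also says that MRD-negative patients will be watched for relapse for 3 years after randomization "by means of rapid reporting as described in section 16.1.1". Section 16.1.1 announces two types of form but describes only the bleeding and atrial fibrillation form.

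**The concern.** The bracket presents itself as a restatement of the rule, yet for one group it says the opposite. An arm B patient back on ibrutinib is due the form under the rule and not due it under the bracket. A data centre that programs its e-mails from the bracket would stop at month 15 for the whole arm.

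Arm A patients would then be asked about bleeding and atrial fibrillation every 3 months, while restarted arm B patients on the same drug would rely on unprompted reporting. A lower recorded AESI frequency in the restarted patients could reflect collection rather than risk. These figures are also used during the trial. Section 14.3 triggers a safety report when an AESI reaches a frequency of 20%, and section 14.4.4 lists AESI beside the number of reinitiated patients in interim analyses IV and V.

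**Working it through.** **Where the 15 months comes from.** Section 9.1 gives 15 induction cycles of 28 days: 15 × 28 = 420 days, or 420 / 30.4375 = 13.8 calendar months. The protocol counts this as 15 months, since it places month 27 at 12 months after stopping. So 15 months is the first ibrutinib exposure, which yields 15 / 3 = 5 quarterly forms. It equals total ibrutinib exposure only for an arm B patient who never restarts.

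**The texts side by side, for a restarted arm B patient.**

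| Place | Is the form due after restart? |
|---|---|
| 16.1.1, general rule | Yes, while on ibrutinib |
| Table 10.2.1, footnote | Yes, same rule, no cap |
| 16.1.1, bracket | No, ends at 15 months |
| Table 10.2.3 | No row for the form |

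Two statements include these patients and one excludes them. The schedule written for them is silent.

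**Forms per patient under the general rule.** Inputs: one form every 3 months (16.1.1); horizons at month 27 (primary analysis), month 51 (end of the 3-year visit schedule) and month 84 (7 years' follow-up, 10.1.1). The restart months are assumptions, as is ibrutinib continuing to each horizon. For a restarted patient, additional forms = (horizon − restart month) / 3. For an arm A patient still on ibrutinib, total forms = horizon / 3.

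| | By month 27 | By month 51 | By month 84 |
|---|---|---|---|
| Arm A, total | 9 | 17 | 28 |
| Arm B under the bracket, total | 5 | 5 | 5 |
| Additional forms due, restart at month 18 | 3 | 11 | 22 |
| Additional forms due, restart at month 21 | 2 | 10 | 21 |
| Additional forms due, restart at month 24 | 1 | 9 | 20 |

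For example, restart at month 18 gives (51 − 18) / 3 = 11. These are prompts not sent, not events missed.

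**What cannot be worked out.** The protocol gives no expected reinitiation rate and no figure for how many events unprompted reporting would catch. The number of patients affected and the size of any under-ascertainment therefore have no basis in the document.

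**The case against.** The strongest defence is that the bracket is only a gloss on the usual course, and that the rule, its repetition in Table 10.2.1 and section 12.1 all cover restarted patients. It shows that the likely intention was to include them. It does not remove the contradiction, because the bracket is the more specific instruction and nothing says which governs.

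A second defence is that the missing row in Table 10.2.3 proves little. In the text available, the Rapid Report Form row of Table 10.2.1 is marked only at the ends of cycles 3 and 6, 9 and 12, so after cycle 15 arm A also depends on the footnote. That is fair. The missing row is therefore not the source of the inequality; it only means that the reinitiation schedule does not resolve it.

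The third defence limits the consequence, and it stands. Under section 12.2.1, adverse events are reported until 30 days after the last dose of any protocol drug, which covers reinitiated treatment. AESI go on a separate form with no limit by arm or period. Sections 10.1 and 10.2 keep quarterly visits in place for 2 years after cycle 15. Section 12.2.1 exempts grade 1 events from reporting, but section 14.4.2 tabulates only grade 2 or more.

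A reader might infer that AESI rates by arm are invalid for comparison. The protocol does not support that: sections 7 and 14 exclude a formal comparison, and section 14.4.6 treats everything except the primary analysis as hypothesis-generating. Moreover, arm B time off drug is unsolicited under the general rule itself, so correcting the bracket alone would not equalise collection between the arms.

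A reader might also infer from the dangling reference in section 7 that relapse in the stopping arm is not monitored. That does not follow either. Sections 10.1, 10.2, 10.6 and 12.10 specify the visits, MRD testing, the one-month retest and real-time follow-up. What is missing is the description of a form.

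**Conclusion.** The contradiction in section 16.1.1 is real and should be corrected. If the bracket is applied, restarted arm B patients lose the quarterly prompt that arm A keeps on the same drug, and a secondary safety endpoint is collected with unequal intensity during ibrutinib exposure. Per patient, that is 1 to 3 forms by month 27 and 9 to 11 by month 51, assuming restart between months 18 and 24 and continued ibrutinib.

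It would be tempting to turn this into a percentage, for instance that AESI rates in restarted patients are 20–50% too low. That figure is only one minus an assumed capture of 50–80% without the prompt. No document supports the assumption, and it takes no account of the AESI form and the scheduled visits. The supportable conclusion is unequal ascertainment of unknown size. The primary endpoint, sample size and error rates are unaffected.

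**What to change.** - In section 16.1.1, reword the bracket so that the form is due during induction, during maintenance and, for arm B, again from reinitiation until ibrutinib ends.
- Add a matching Rapid Report Form row to Table 10.2.3.
- In section 14.4.2, tabulate AESI after cycle 15 by time on ibrutinib, since arm B time off drug stays unsolicited.
- As a minor editorial item, reconcile the section 7 cross-reference and the announcement of two forms with the single form described: either describe the relapse form or point section 7 to where the monitoring is specified.

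The cost is wording plus a few more quarterly e-mail forms for restarted patients, using a form already in operation. No dose, visit or clinical rule changes.
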